2.2. Treatment Phase

Study Schedule Protocol H8H-MC-LAHB: Treatment Phase

Procedure	Treatment Phase: Periods 1-5				Follow-up Phase	Comment
Study Day	-1	1	2	D/C or ET	20	Minimum of 3 days = 72 h washout between doses
Visits	I	I	I		O	I: inpatient; O: outpatient; Follow-up = approximately 1 week after last dose of study drug.
Weight	X			X	X	Weight will be collected at Treatment Phase Period 1, D/C or ET, and Follow-up.
ECG	X	0, 2, 4	24	X	X	
Study Drug Dosing		X				Study drug will be administered on Day 1 after an overnight fast.
AE/Medication Review	X	X	X	X	X	
PE	X					Full PE at first CRU admission. Symptom-driven PE at all other time points as deemed necessary by PI.
BP/Pulse	X	0, 1, 2, 4, 6	24	X	X	Single supine BP and pulse rate. Follow same window as PK.
Urine Drug Screen and Alcohol Screen	X				X	Urine Drug and Alcohol screen will be collected at Treatment Phase Period 1 and Follow-up (additional test will be performed at Periods 2-5 if subject discharged between periods).
Pregnancy Test	X				X	Pregnancy test will be collected at Treatment Phase Period 1 only and Follow-up (additional test will be performed at Periods 2-5 if subject discharged between periods).
CBC and Chemistry	X				X	Fasting samples on Days -1 of all periods.
VAS training	X					VAS training to occur on Day -1 of each Period
Drug Effects Battery		0, 0.25, 0.5, 1, 1.5, 2, 2.5, 3, 3.5, 4, 4.5, 5, 6, 8, 12	24			Overall Drug Liking and Take Drug Again assessed at 12 and 24 hours postdose only.
Drug Similarity VAS Battery			24			
C-SSRS/ Self-Harm	X			X	X	A self-harm form may be administered at time of C-SSRS. C-SSRS/Self Harm will be administered on Day -1 Treatment Phase Period 1, D/C or ET, and Follow-up (additional test will be performed at Periods 2-5 if subject discharged between periods).
PK		0, 0.5, 1, 1.5, 2, 2.5, 3, 4, 6, 8, 12	24			
Genetic Sample	X					Genetic samples will be collected at the first period of Treatment Phase only.

Abbreviations: AE = adverse event; BP = blood pressure; CBC = complete blood counts; CRU = clinical research unit; C-SSRS = Columbia-Suicide Severity Rating Scale; D/C = discontinuation; ECG = electrocardiogram; ET = early termination; h = hour; PE = physical examination; PI = principle investigator; PK = pharmacokinetics; VAS = visual analogue scale.

Note: if multiple procedures take place at the same time point, the following order of the procedure should be used: ECG, vital signs, and venipuncture.

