10.3.3. Abuse Potential Analyses

Descriptive statistics for the Drug Liking VAS will be reported for each treatment and for each paired difference among treatments. A linear mixed-effects model, which includes period, sequence, and treatment as fixed effects, and subject as a random effect will be used to evaluate the hypothesis tests of primary interest at the peak of drug response effects (E_{max}) at a significance level of 0.05 (1-sided). The following pairwise comparisons will be made:

- alprazolam minus placebo, with null hypothesis that the difference is ≤ 15 mm;
- alprazolam minus each dose of lasmiditan, with the null hypothesis that the difference is ≤ 5 mm; and

- each dose of lasmiditan minus placebo, with the null hypothesis that the difference is ≥ 14 mm.

Least square mean estimates and 90% confidence intervals will be reported for each treatment and for each paired difference among treatments.

The residuals from the mixed-effect model will be investigated for normality using the Q-Q plot. If this normality assumption is not met, paired sample t-test or nonparametric test will be considered based on actual data distributions. For nonparametric analyses, pairwise treatment comparisons will be assessed using the Wilcoxon signed-rank test on the within-subject differences, and median and intraquartile range will be reported.

Descriptive statistics for each other element of the Drug Effects VAS Battery, aside from Drug Liking VAS, and for time to peak effect will be reported for each treatment. If the normality assumptions of mixed-effects model on the residuals are met, a linear mixed-effects model, which includes period, sequence, and treatment as fixed effects, and subject as a random effect will be used to provide least square mean estimates and 90% confidence intervals for each treatment. The residuals from the mixed-effect model will be investigated for normality using the Q-Q plot. If the normality assumptions of mixed-effects model are not met, alternative approaches such as paired t-test or non-parametric test may be considered based on the actual data distributions. For non-parametric analyses, the median and intra-quartile range will be reported for each treatment.

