9.4 Pharmacodynamic Assessment

9.4.1 Pharmacodynamic Analysis

Drug Effects VAS Battery lists a series of Drug Effects VAS measures that evaluate different subjective effects of the abuse potential of the study drug as shown in the table below.

Scale Name	Scale Text	Response Anchors
Drug Liking	At this moment, my liking for this drug is	0: Strong disliking 100: Strong liking
Overall Drug Liking	Overall, my liking for this drug is	
Take Drug Again	I would take this drug again	0: Definitely not 100: Definitely so
Good Effects	I can feel good drug effects	
Bad Effects	I can feel bad drug effects	
Alertness/Drowsiness	I am feeling	0: Very drowsy 100: Very alert
Agitation/Relaxation	My mood is	0: Very relaxed 100: Very agitated
High	I am feeling	0: Not at all high 100: Extremely high
Hallucination	I am experiencing hallucinations	0: Not at all 100: Extremely

The primary objective of the study is to assess the abuse potential of lasmiditan compared to the positive control alprazolam and to placebo using the maximal effect score (E_{max}) of the at-the-moment 100 mm bipolar Drug Liking VAS. The bipolar Drug Liking VAS is consistent with FDA Guidance (January 2017)³ such that placebo should produce a score between 40 and 60 representing neutral drug-liking (ie, neither like nor dislike); a score of 0 indicates strong disliking, and a score of 100 indicates strong liking.

The remaining questions in the Drug Effects VAS Battery and the Drug Similarity VAS Battery will be assessed as secondary endpoints.

The Drug Similarity VAS Battery is composed of two sets of VAS measures, the baseline set of VAS measures is to determine how familiar the subjects are with various drugs and how similar their most recently received drug is to those. The second set of VAS measures is confined to checking how similar the most recent drug received was to a list of various drugs. The Baseline set of VAS battery questions will be administered in the Qualification Phase and the second set of measures will be administered during the Treatment Phase. In the tables below are the proposed Drug Similarity VAS measures of interest.

Drug Similarity Visual Analog Scale Battery – Baseline	
1	How familiar are you with cocaine (including crack) use? (not applicable)
2	How similar is the drug you most recently received to cocaine (including crack)? (not applicable)
3	How familiar are you with caffeine use? (not applicable)

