9.4.2 Pharmacodynamic Statistical Methodology

Descriptive statistics for the Drug Liking VAS will be reported for each treatment and for each paired difference among treatments.

The E_{max} will be derived as the maximum at-the-moment Drug Liking VAS score among all the individual values that are collected at the scheduled assessment timepoints. The time to E_{max} is the corresponding timepoint at which the maximum score occurs. These will be derived for both the Qualification Phase and Treatment Phase separately for each treatment.

A linear mixed-effects model, which includes period, sequence, and treatment as fixed effects, and subject as a random effect will be used to evaluate the hypothesis tests of primary interest at the E_{max} at a significance level of 0.05 (1-sided). The following pairwise comparisons will be made:

- Alprazolam minus placebo, with null hypothesis that the difference is ≤ 15 mm;

- Alprazolam minus each dose of lasmiditan, with the null hypothesis that the difference is ≤ 5 mm; and
- each dose of lasmiditan minus placebo, with the null hypothesis that the difference is ≥ 14 mm.

Least square mean estimates and 90% confidence intervals (CI) will be reported for each treatment and for each paired difference among treatments.

An example of the SAS code that will be used is as follows:

```
proc mixed data=xxxx;
class trtmnt period sequence subject;
model emax = trtmnt period sequence / ddfm=kr alpha=0.1 residual outp=pred;
random subject;
lsmeans trtmnt / pdiff=control alpha=0.1; /*Produce 90% CI*/
lsmeans trtmnt / pdiff=controll alpha=0.05; /*Test at 0.05 significance 1-sided*/
ods output lsmeans=lsml1;
ods output diffs=diff1;
run;

/* Wilcoxon signed rank test */
proc univariate data=tmax;
  var result;
  ods output Quantiles=quant;
  ods output TestsforLocation=pvalues(where=(test='Signed Rank'));
run;

/* Paired sample t-test */
proc ttest data=all;
  title "Paired sample t-test";
  paired Control * Treatment;
run;
```

In the example SAS code, this is currently presenting a lower-tailed test, however this may need adjusting for some of the comparisons.

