The residuals from the mixed-effect model will be investigated for normality using the Q-Q plot. If this normality assumption is not met, paired sample t-test or nonparametric test will be considered based on actual data distributions. For nonparametric analyses, pairwise treatment comparisons will be assessed using the Wilcoxon signed-rank test on the within-subject differences, and median and interquartile range will be reported.

Descriptive statistics for each other element of the Drug Effects VAS Battery, aside from the Drug Liking VAS, and for time to peak effect will be reported for each study phase and treatment. If the normality assumptions of mixed effects model on the residuals are met, a linear mixed-effects model similar to that employed for the E_{max} of Drug Liking VAS will be employed for each other element of the Drug Effects VAS Battery.

Descriptive statistics for each element of the Drug Similarity Visual Analog Scale Battery – Baseline and Drug Similarity Visual Analog Scale Battery will be reported for each study phase and treatment.

The pattern of missing data will be assessed in the population of patients who entered into the treatment phase and took at least 1 dose of study drug in the treatment phase by looking at the trend of dropout rates among the first 4 periods, as well as comparing the dropout rates among the 5 treatments.

A sensitivity analysis will be performed on all patients who entered into the treatment phase and received at least 1 dose of study drug in the treatment phase, regardless of completion of all the 5 periods. The same mixed model and model diagnosis procedure as the primary analysis will be implemented.

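### The planned model for Alertness/Drowsiness and Agitation/Relaxation leaves out the 0 h score collected in each period, which costs some precision on two secondary scales

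*SAP*

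**What the plan says.** **Data collected.** Under a header that covers Treatment Phase Periods 1 to 5, Protocol 2.2 schedules the Drug Effects battery at "0, 0.25, 0.5, 1, 1.5, 2, 2.5, 3, 3.5, 4, 4.5, 5, 6, 8, 12" hours on Day 1 and again at 24 h. The only exemption is "Overall Drug Liking and Take Drug Again assessed at 12 and 24 hours postdose only". Alertness/Drowsiness and Agitation/Relaxation therefore have a pre-dose score in all five periods.

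**Nature of the scales.** SAP 9.4.1 words these two items as the subject's present feeling and mood. The drowsy end of the first scale is 0, and the low anchor of the second is "0: Very relaxed".

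**Model.** SAP 9.4.2 says of the other battery elements: "If the normality assumptions of mixed effects model on the residuals are met, a linear mixed-effects model similar to that employed for the" Drug Liking maximum will be used. The code for that model reads "model emax = trtmnt period sequence / ddfm=kr alpha=0.1 residual outp=pred" with "random subject". Protocol 10.3.3 spells out the terms for the other elements itself: a model "which includes period, sequence, and treatment as fixed effects, and subject as a random effect will be used to provide least square mean estimates" with 90% intervals. Neither document names a baseline term.

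**Baseline elsewhere.** SAP 9.1 explains how a change from baseline is computed, but the only baseline that the SAP defines is for vital signs (9.5.5).

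**Response.** The only derivation that SAP 9.4.2 gives is for Drug Liking: the maximum over all scheduled time points. It gives no summary measure for the two state scales.

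**The concern.** A rating of how alert or how agitated someone feels means something before any drug is given, so the 0 h score is a real baseline for that period. A random subject intercept absorbs how drowsy or tense a subject is on average. It does not absorb a poor night before Period 3. That departure reaches the post-dose score to some degree and is counted as error, although it was measured.

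What is at stake is the width of the intervals on two secondary scales. They are not idle measures: Protocol 5.4.2 gives sedative effects as lasmiditan's predominant adverse events and as part of the reason for choosing alprazolam. Alertness/Drowsiness bears directly on that comparison; Agitation/Relaxation, a mood item, bears on it less directly.

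**Working it through.** **1. The plan's own figure.** No power is stated for these two scales. The stated power of 90% or more is for Drug Liking (Protocol 10.1: SD of differences 16, about 50 completers, one-sided 0.05). Each assumed mean lies 7 mm from its margin: 22 − 15, 12 − 5, 14 − 7.

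- SE = 16/√50 = 2.263
- Power = Φ(7/2.263 − 1.645) = Φ(1.449) = 92.6%

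The stated power is reproduced, and nothing below changes it.

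**2. Reference interval.** The documents give no SD for the two state scales, so the Drug Liking SD is borrowed as an illustration. Residual degrees of freedom are 250 − 50 − 4 − 4 = 192, and the 90% half-width is 1.653 × 2.263 = 3.74 mm.

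**3. With the period's 0 h score as covariate.** Let r be the within-subject correlation between a period's 0 h score and its post-dose score. The residual variance is multiplied by 1 − r². The documents give no r, so a range is assumed, with the same r on every treatment.

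| r | SE ratio √(1 − r²) | SE reduction | 90% half-width (mm) | Equivalent completers 50/(1 − r²) |
|---|---|---|---|---|
| 0 | 1.000 | 0% | 3.74 | 50 |
| 0.2 | 0.980 | 2.0% | 3.66 | 52 |
| 0.3 | 0.954 | 4.6% | 3.57 | 55 |
| 0.4 | 0.917 | 8.3% | 3.43 | 60 |
| 0.5 | 0.866 | 13.4% | 3.24 | 67 |
| 0.6 | 0.800 | 20.0% | 2.99 | 78 |

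Simulation of the ten printed sequences with 50 subjects gave ratios of about 0.98, 0.96, 0.92, 0.87 and 0.80 for r = 0.2 to 0.6, with no bias with or without the covariate. At r = 0 the covariate cost about 0.3% of the SE.

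**4. If r differs between treatments.** Scores pushed towards the end of the scale would weaken r on active drug. With one common slope near the average r̄, the variance factor for treatment t is 1 − 2·r_t·r̄ + r̄², and a contrast averages its two factors.

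- Placebo 0.5, the other four 0.1 (r̄ = 0.18). Placebo: 1 − 0.18 + 0.032 = 0.852. Others: 1 − 0.036 + 0.032 = 0.996. Against placebo the SE ratio is √0.924 = 0.961, a 4% reduction. Between two active treatments it is √0.996, practically none.
- Placebo 0.5, then 0.4, 0.3 and 0.2 for rising lasmiditan doses, alprazolam 0.1 (r̄ = 0.3). Alprazolam against placebo: √((1.03 + 0.79)/2) = 0.954, a 5% reduction. Alprazolam against 400 mg: √((1.03 + 0.97)/2) = 1.00, none.

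**5. Covariate or change score.** With equal variances at 0 h and post-dose, subtracting the 0 h score multiplies the variance by 2(1 − r), which exceeds 1 when r < 0.5. At r = 0.3 the half-width is 3.74 × √1.4 = 4.43 mm, wider than with no baseline at all.

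**6. What the response would be.** If the Drug Liking derivation is carried over unchanged, the value for Alertness/Drowsiness is the highest score over all time points, 0 h included. With 0 as the drowsy end, that is the most alert moment and may be the pre-dose score itself. The covariate would then be part of the outcome, so the response has to be settled first.

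**7. Carryover into the 0 h score.** Protocol 5.4.2 gives alprazolam a mean half-life of 11.2 h, range 6.3 to 26.9 h. After the minimum 72 h washout, 0.5^(72/11.2) = 1.2% remains at the mean and 0.5^(72/26.9) = 16% at the longest. Each ordered pair of treatments occurs exactly twice across the ten sequences, so first-order carryover is balanced, but it is not ruled out.

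**The case against.** The planned model is valid. The scales are secondary, with no hypothesis, margin or power attached, and no conclusion of the trial rests on their intervals. That stands, and it makes this an improvement in precision and not the correction of an error.

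The benefit is also unproven. The simulation returns √(1 − r²) because that relation was built into it, so it confirms the arithmetic for this design and says nothing about r in these subjects. The design already limits variation between mornings: admission on Day −1, an overnight fast, no alcohol for 24 h before visits, and dosing at about the same time. Against that, the Protocol allows discharge between periods and, at the investigator's discretion, continuation after a positive cannabinoid test. A gain of 0% to 5% is as compatible with the documents as one of 13% to 20%.

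Two additions would be superfluous. The Drug Liking model already reports 90% intervals for paired differences, and a similar model for these scales carries that over. In completers, the subject's mean 0 h score does not affect within-subject treatment contrasts.

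A reader might infer that the plan discards the 0 h ratings. It does not: the time course is a listed secondary endpoint and both documents allow further analyses. Only the model omits them. A reader might also hope that the SAP's word for the model, similar, leaves room for a baseline term. The Protocol's explicit list of terms for these elements contains none, and SAP section 11 reports no change from the Protocol.

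**Conclusion.** The point holds as a modest, low-priority one. The model for these two scales leaves the morning's departure from the subject's usual state in the error term, although it is measured in every period. Under an assumed common correlation of 0 to 0.6, adjustment lowers the SE of a treatment difference by 0% to about 20%. It lowers it by less, and for contrasts between active treatments perhaps not at all, if the correlation weakens under sedation. These figures also rest on equal within-subject variance across treatments; the half-widths in mm borrow the Drug Liking SD.

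Two stronger readings are not supported. The omission does not bias the treatment comparisons: period and treatment are balanced over the sequences, and the estimates are unbiased either way. Nor does it weaken the primary analysis: the Drug Liking model, its margins and its reproduced power of about 92% are unaffected.

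**What to change.** In SAP 9.4.2, for Alertness/Drowsiness and Agitation/Relaxation only:

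1. Define the response from post-dose time points, with 0 h excluded, in the direction of the effect of interest, for example the minimum (towards very drowsy or very relaxed).
2. Add the period's 0 h score, as its deviation from the subject's mean 0 h score over the Treatment Phase, as a covariate. Do not use a change score. The subject's mean 0 h score may be added as a second term; it is optional in completers.
3. State how a period with a missing 0 h score is handled, so that it does not silently drop out of the model.
4. Summarise the 0 h scores by preceding treatment as a check for carryover before relying on the adjustment.

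Leave the Drug Liking model as it is.

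The cost is one or two degrees of freedom and a few lines of text and code; no new data, visits or subjects are needed. The covariate has no place in a paired t-test or Wilcoxon test, so if the Protocol's fallback for non-normal residuals is used, that analysis stays unadjusted. The SAP should say so.

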9.5 Safety and Tolerability Assessments

9.5.1 Adverse events

Where changes in severity are recorded in the Case Report Form (CRF), each separate severity of the AE will be reported in the listings, only the most severe will be used in the summary tables. A pre-existing condition is defined as an AE that starts before the subject has provided written informed consent and is ongoing at consent. A non-treatment emergent AE is defined as an AE which starts after informed consent but prior to first dosing of the Qualification Phase. A treatment-emergent AE is defined as an AE which occurs postdose or which is present prior to dosing and becomes more severe postdose.

All AEs will be listed. Treatment-emergent AEs will be summarized by treatment, severity and relationship to the study drug. The frequency (the number of AEs, the number of subjects experiencing an AE and the percentage of subjects experiencing an AE) of treatment-emergent AEs will be summarized by treatment, Medical Dictionary for Regulatory Activities (MedDRA) version 20.0 system organ class and preferred term. The summary and frequency AE tables will be presented for all causalities and those considered related to the study drug. Any serious AEs will be tabulated. All AE outputs will be presented by Qualification Phase and Treatment Phase separately. An AE that starts during the Qualification Phase or before the Treatment Phase start will be presented under the Qualification Phase summaries only. In the Treatment Phase outputs, any AEs that are ongoing from the Qualification Phase will be flagged in listings, and excluded from tables.

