10.3.1. Safety Analyses

10.3.1.1. Clinical Evaluation of Safety

All investigational product and protocol procedure AEs will be listed by treatment, and if the frequency of events allows, safety data will be summarized using descriptive methodology.

The incidence of symptoms for each treatment period will be presented by severity and by association with the investigational product as perceived by the investigator. Symptoms reported to occur prior to study entry will be distinguished from those reported as new or increased in severity during the study. Each symptom will be classified by the most suitable term from the Medical Dictionary for Regulatory Activities (MedDRA).

The number of investigational product-related SAEs will be reported by treatment.

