legal representative	An individual or a judicial or other body authorized, under applicable law, to consent, on behalf of a prospective subject, to the subject's participation in the clinical study.
Lilly	Eli Lilly and Company
LY573144	lasmiditan (also COL-144)
MedDRA	Medical Dictionary for Regulatory Activities
OTC	over-the-counter
QTc	corrected QT interval
randomization	The process of assigning subjects/patients to an experimental group on a random basis.
RBC	red blood cell
PK	pharmacokinetic
SAE	serious adverse event
screen	The act of determining if an individual meets minimum requirements to become part of a pool of potential candidates for participation in a clinical study.
SUSARs	suspected unexpected serious adverse reactions
TBL	total bilirubin level

Term	Definition
TEAE	treatment-emergent adverse event: Any untoward medical occurrence that emerges during a defined treatment period, having been absent pretreatment, or worsens relative to the pretreatment state, and does not necessarily have to have a causal relationship with this treatment
T_{max}	time after administration of drug when maximum plasma concentration is reached; rate of absorption equals the rate of elimination
TQT	thorough QT study
ULN	upper limit of normal
VAS	Visual Analog Scale
WBC	white blood cell
WOCBP	woman/women of childbearing potential

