9.5.5 Vital signs

Vital signs data will be summarized by study phase and treatment together with changes from baseline, where baseline is defined as Day 1 predose for each study phase separately. Figures of mean vital signs and mean changes from baseline profiles by treatment will be presented by study phase and treatment. Furthermore, values for individual subjects will be listed by study phase.

Changes from baseline (predose) will be calculated for vitals signs.

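### SAP 9.5.1 keeps an AE carried over from Qualification out of the Treatment Phase tables even if it worsens after a Treatment Phase dose, contrary to its own definition of treatment-emergent

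*SAP*

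**What the plan says.** SAP section 9.5.1 contains five rules that bear on this point.

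- **Definition.** "A treatment-emergent AE is defined as an AE which occurs postdose or which is present prior to dosing and becomes more severe postdose". The wording is not tied to one phase.
- **Tabulation.** "Treatment-emergent AEs will be summarized by treatment, severity and relationship to the study drug".
- **Severity.** Where the CRF records a change in severity, "each separate severity of the AE will be reported in the listings, only the most severe will be used in the summary tables".
- **Phase assignment.** "An AE that starts during the Qualification Phase or before the Treatment Phase start will be presented under the Qualification Phase summaries only".
- **Exclusion.** "In the Treatment Phase outputs, any AEs that are ongoing from the Qualification Phase will be flagged in listings, and excluded from tables".

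The same section also asks for a tabulation of any serious AE and splits all AE outputs by phase.

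In the protocol, the Appendix 1 definition covers an event that "emerges during a defined treatment period, having been absent pretreatment, or worsens relative to the pretreatment state". Section 10.3.1.1 adds: "The incidence of symptoms for each treatment period will be presented by severity". Table LAHB.1 lists the treatment-emergent AE profile among the secondary endpoints. SAP section 11 declares no departure from the protocol's analyses.

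**The concern.** The definition and the last two sentences of 9.5.1 give opposite instructions for one kind of event: an AE that began before the Treatment Phase, is still present when that phase starts, and becomes more severe after a Treatment Phase dose. The definition and the tabulation rule put it in the table for the treatment just taken. The phase rule and the exclusion take it out.

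The table at stake reports a named secondary endpoint. A programmer following the exclusion literally would produce a by-treatment table that does not match the definition given for it. The severity rule adds a second problem. If the AE is shown only under Qualification, at its most severe grade and with no cut-off date, a grade reached after a Treatment Phase dose could be displayed under 1 mg alprazolam or placebo from Qualification.

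**Working it through.** The plan states no figure to reproduce, so the check is a reading of the rules against each other, followed by one count from the design figure.

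**1. One event traced through SAP 9.5.1.** A subject has a mild AE with onset after a Qualification dose. It is still mild before the first Treatment Phase dose and becomes moderate after a Treatment Phase dose.

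| Rule in 9.5.1 | Result for this event |
|---|---|
| Definition | Treatment-emergent with respect to the Treatment Phase dose, because it was present before that dose and worsened after it |
| Tabulation | Belongs in that treatment's table, as moderate |
| Phase assignment (by start date) | Qualification summaries only |
| Exclusion | Flagged in Treatment Phase listings, absent from Treatment Phase tables |
| Severity (worst grade, no cut-off) | On one reading, shown as moderate under a Qualification treatment |

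The first two rows cannot be satisfied together with the third and fourth. No other section of the SAP or protocol supplies an exception.

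**2. Comparison with the protocol.** Appendix 1 measures worsening against the state before treatment, within a defined treatment period. The traced event meets that definition for the Treatment Phase treatment. Section 10.3.1.1 also points to incidence by treatment period and severity, but this support is limited: that section makes the safety summaries depend on the frequency of events, and its explicit contrast is with symptoms before study entry, not between phases.

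**3. Comparison within the SAP.** Section 9.5.5 resets the reference for vital signs by phase ("where baseline is defined as Day 1 predose for each study phase separately"). Section 9.5.1 gives no matching reset for AE severity. This is a contrast only, since a change-from-baseline rule does not set the standard for AE onset.

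**4. Serious AEs.** If such an event became serious in the Treatment Phase, one sentence of 9.5.1 would require it to be tabulated and another would exclude it from the Treatment Phase tables. The section does not say which prevails.

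**5. How far the rule reaches.** Each subject who completes receives 2 + 5 = 7 doses, which gives 6 between-dose intervals: 1 within Qualification, 1 from Qualification to Treatment, and 4 between Treatment Phase periods. The rule concerns AEs open at the end of the one interval that crosses the phases. It works on start date, so an AE that begins late in that washout is caught too, and neither the 72-hour minimum nor a half-life bounds its reach.

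**6. Direction.** Counting down each Treatment Phase column of the design figure, placebo, alprazolam and the three lasmiditan doses each appear in 2 of the 10 sequences in every period, Period 1 included. The exclusion is the same for all five treatments, so the design gives no reason to expect that it favors one of them.

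**The case against.** The best defense is that 9.5.1 first defines which AEs are treatment-emergent across the whole study and then allocates each one once, by onset, to a phase. On that view an AE that began after a Qualification dose is already treatment-emergent and already appears in a Qualification table, so nothing is lost. Part of this stands: the event does appear in a Qualification summary and is flagged in the Treatment Phase listings. But the allocation leaves the worsening half of the definition without effect in the Treatment Phase tables for any AE that began earlier. Counting by onset alone would also depart from Protocol Appendix 1, while SAP section 11 declares no departure.

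A second defense is that the site may enter a worsening as a new AE with its own start date. The SAP does not say so, and its opening sentence on AEs treats severity changes as grades of one AE.

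A third is that the table shells, which the SAP mentions and which were not available, may settle the matter. They may, but the SAP text would still conflict with itself.

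A fourth is that such events will be rare. That is plausible: dosing is single-dose with at least 72 hours between doses, Protocol 6.1.1 requires tolerance of the 1-mg alprazolam test dose, and Protocol 8.1 takes subjects with an SAE, or with certain sustained AEs, off study drug. This limits the size of the problem without removing the conflict.

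In the other direction, a reader might infer that the rule hides harm from lasmiditan or loses safety data. The documents do not support either inference. The rule is the same for every treatment, treatments are balanced over periods, and the events remain flagged in the listings.

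**Conclusion.** The conflict is real and lies within SAP 9.5.1. Applied exactly, the exclusion removes from a treatment's AE table an event that the SAP and Protocol Appendix 1 both define as treatment-emergent for that treatment. That the worsened grade could appear under a Qualification treatment is a possible reading, not a certain one.

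The size is minor. The documents do not give the number of such events, and it may be zero. Safety analysis is descriptive (SAP 9.5.9), no bias between treatments is shown, and the primary Drug Liking analysis is unaffected. The conclusion rests on two assumptions: that a worsening is recorded as a grade change of one AE, as the SAP's severity sentence implies, and that the table shells contain no exception.

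**What to change.** In the last sentence of SAP 9.5.1, after the exclusion from tables, add: *unless they become more severe after a Treatment Phase dose, in which case they are also tabulated as treatment-emergent, at the worsened severity, under the treatment most recently taken.* Make the preceding sentence, which restricts such AEs to the Qualification summaries, subject to the same exception. State that Qualification tables use the worst severity before the first Treatment Phase dose.

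The cost is a few lines of SAP text and a small derivation. Two consequences should be accepted openly. The derivation needs dated severity changes on the CRF, and the SAP is conditional on whether such changes are recorded at all. One AE can then appear in both phases, so AE counts must not be added across phases, and a table footnote should say so.
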